10.3.2.2 Analysis for secondary variables

For the analysis of these variables, the same primary analysis will be carried out as long as they have the necessary measurements to do so.

10.3.3 Exploratory Analysis

The analysis of exploratory variables will be carried out in those subjects who conclude their participation without deviations from the study protocol (population by protocol, PP). The same primary analysis will be carried out if they have the necessary measurements to do so.

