3.1.2.3 Exploratory

- To assess the safety of PRO-201 ophthalmic solution applied to the ocular surface in healthy volunteers, by assessing best-corrected visual acuity (BCVA).
- To evaluate the safety of PRO-201 ophthalmic solution applied to the ocular surface in healthy volunteers, by assessing intraocular pressure (IOP).
- To evaluate the safety of PRO-201 ophthalmic solution applied to the ocular surface in healthy volunteers, by evaluating corneal and conjunctival staining with fluorescein and lysmine green.
- To assess the safety of PRO-201 ophthalmic solution applied to the ocular surface in healthy volunteers, by assessing vital signs (heart rate and blood pressure).
- To evaluate the tolerability of PRO-201 ophthalmic solution by means of the Ocular Comfort Index (OCI) score.

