5.2 Criteria for elimination and/or substitution of subjects

5.2.1 Elimination Criteria

- Withdrawal of the letter from the FCI.
- Presentation of a serious adverse event related or not to the investigational product, which at the discretion of the PI and/or sponsor could affect the patient's ability to continue with the study procedures safely.
- No tolerability or hypersensitivity to any of the compounds used during the tests (fluorescein, lysmine green or tetracaine).
- No tolerability or hypersensitivity to any of the investigational drugs.
- Adherence < 90% determined by the subject's diary

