6.4 Procedure for monitoring and measuring adherence

For more than four decades, there has been a lot of research on the appropriate way to measure and quantify medication adherence, but none has reached a consensus to stand as the gold standard, both in cross-sectional and longitudinal studies. [27, 28, 29, 30, 31, 32, 33, 34]

There are different procedures to measure adherence to pharmacological interventions. The most common procedure includes self-reports, which include patient interviews, questionnaires and self-monitoring diaries. Its strengths are speed, flexibility, low cost and ease of implementation; They have a high degree of specificity for non-adherence, however, the sensitivity and reliability for adherence is low. [34, 35]

The biochemical measurement of the drug, or its metabolite, is one of the methods that best confirms the use of the drug. However, in addition to raising costs and being impractical, it is of little use in the context of ophthalmic applications, since concentrations at the peripheral level could be undetectable; and samples of other tissues involve more invasive methods that would not be advisable. [34]

There is no standardized parameter to define adequate adherence, it must be defined and delineated by the objectives of the research. [34]

For this study, a minimum adherence of 90% (per subject's diary) will be necessary to meet the objectives of the research. Therefore, subjects with adherence of less than 90% will not be considered for the evaluation of exploratory variables but will be considered for the safety and tolerability variables in the intention-to-treat population group.

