8.2 Definition of Adverse Event

According to the International Council on Harmonization (ICH), an adverse event (AE) is any unfavorable medical appearance in a clinical investigational subject who is administered a pharmaceutical product, regardless of causal attribution. [47] [48] [49]

Therefore, an AE can be any of the following: any unfavorable and unintentional disease, symptom, or sign (including an abnormal laboratory finding) that is temporally related to the use of a medical product, whether or not it is considered related to such a product; any new illness or exacerbation of an existing disease (worsening of the nature, frequency, or severity of a known condition); relapse of an intermittent medical condition (e.g., headache) not present at baseline; any deterioration in a laboratory value or other clinical test (e.g., electrocardiogram [ECG], x-ray) that is related to symptoms or that results in a change in study treatment or concomitant treatment or discontinuation of study medication. [47] [48] [49]

As defined in the previous paragraph, an adverse event is defined as any event that occurs during treatment with a drug or device. However, the definition can also be applied as any unwanted event that occurs during a clinical trial, including behavioral disorders. [49]

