8.5.2.4 Abnormal vital signs

Not all abnormal vital signs qualify as AE. For an abnormal vital sign to be reported as an AD, it must meet any of the following criteria:

Be accompanied by clinical symptoms. It results in a change in treatment (dose modification, treatment interruption, etc.).

The report on abnormal values should focus on obtaining a diagnosis and not just a description of the abnormality.

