10.3.1 Population Analysis

The statistical analysis will be presented to give a general summary of the subjects entered the study and a view of the safety and tolerability of its results. The data provided by the research site will be summarized for this purpose, according to its nature. The Shapiro-Wilk test will be performed to find out if the quantitative data are distributed in a normal way ($p>0.05$).

The results of the quantitative variables will be presented in measures of central tendency: mean, standard deviation, maximum and minimum. Changes in pupillary diameter, near visual acuity, BCVA and OCI will be expressed as continuous variables. Changes in IOP, HR, systemic blood pressure, and TF will be expressed as discrete variables.

The result of the nominal and ordinal qualitative variables will be presented in frequencies, proportions and/or percentages. For these, 2 x 2 frequency tables will be built. All percentages will be presented with decimal.

The level of difference to consider significance will be an alpha (α) of 0.05 or less. The triangulation between the variable type and the measurements is shown in the Board 4 Triangulation of concepts.

Board 4 Triangulation of concepts

Variable Type	Variable	A1	A2	B1	C1	C2	D1	D2	D3	E1	E2	E3	E4	E5
Selection														
A1	Demographic			D										
A2	Medical History/Selection Criteria				D									
Basal														
B1	Comprehensive ophthalmological evaluation			DT	D	TB			TB					
Safety & Tolerability														
C1	Incidence of AE*				TB			TB						
C2	Incidence of photophobia				TB	TB		TB			T			
Secondary Security Outcome														
D1	Pupillary diameter					B	TB							
D2	Incidence of AD				TB	TB		TB						
D3	Near visual acuity			D			TB	B						
Exploratory														
E1	BCAV			D			TB		B					
E2	PIO			D			TB		B					
E3	Corneal and conjunctival stains with fluorescein and lysmine green			D			TB			B				
E4	Vitals signs			D			TB			B				
E5	OCI			D							B			

Abbreviations: BCVA, best corrected visual acuity; B, bivariate analysis; D, descriptive statistics; AE, adverse event; OCI, ocular comfort index; M, multivariate analysis; IOP, intraocular pressure; T, 2x2 contingency table. *Unexpected-related AEs.

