10.3.2 Safety and tolerability analysis

10.3.2.1 Analysis for Primary Variables

An analysis of safety and tolerability outcomes will be carried out in the safety population, defined as any subject who has received at least one dose of the investigational product (PRO-201) regardless of adherence to it or adherence to the protocol (intention-to-treat population, ITT).

The statistical analysis for the primary variables of a quantitative type will be estimated by means of the Kolmogorov-Smirnov statistic for the difference in measurements, once the values have been adjusted with respect to their baseline within everyone. In cases where applicable, the nonparametric Mann-Whitney U test will be used.

For conjunctival hyperemia, Pearson's X² or Fisher's exact test will be used at expected values less than 5.

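### Five measures stated as safety or tolerability objectives are analysed only in completers without deviations, so the numerical values of excluded subjects are left out

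*Combined protocol and SAP*

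**What the plan says.** Section 3.1.2.3 lists five exploratory objectives. Four concern safety: distance BCVA, IOP, corneal and conjunctival staining, and vital signs. The fifth is "To evaluate the tolerability of PRO-201 ophthalmic solution by means of the Ocular Comfort Index (OCI) score".

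Section 10.3.3 sets the analysis population: "The analysis of exploratory variables will be carried out in those subjects who conclude their participation without deviations from the study protocol". It labels this per-protocol (PP). Section 6.4 adds that "subjects with adherence of less than 90% will not be considered for the evaluation of exploratory variables", yet in the same sentence keeps those subjects for the safety and tolerability variables in the intention-to-treat group.

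The elimination criteria in 5.2.1 include "No tolerability or hypersensitivity to any of the investigational drugs", serious adverse events judged to prevent safe continuation, intolerance of the examination agents, and adherence below 90%.

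Section 10.3.2.1 reads differently: "An analysis of safety and tolerability outcomes will be carried out in the safety population", meaning everyone dosed at least once, whatever their adherence. Section 10.3.2.2 carries that analysis over to the secondary variables.

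Section 10.3.1 fixes the outputs: "The results of the quantitative variables will be presented in measures of central tendency: mean, standard deviation, maximum and minimum". It names BCVA, OCI, IOP, heart rate, blood pressure and fluorescein staining among the variables concerned and speaks of summarising those who entered the study, but names no analysis set.

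**The concern.** A safety measure is normally shown for everyone exposed. Here a subject who cannot tolerate the product may be eliminated, and then does not appear in the IOP, acuity, staining, vital-sign or OCI results. Where the reason for leaving relates to the measure, the remaining mean may look better than the experience of all dosed subjects, and the reported maximum and minimum omit the people of most interest. Other reasons for exclusion, such as missed doses, dye intolerance or visit windows, have no fixed direction.

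The plan also gives more than one answer. By 3.1.2.3 these five are safety and tolerability measures, so 10.3.2.1 and the second half of the sentence in 6.4 would put them in the all-dosed set. Section 10.3.3 and the first half of that sentence take them out.

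**Working it through.** **1. The plan's own numbers.** Section 10.1.2 starts from 24 subjects and adds 20%: 24 x 1.20 = 28.8, rounded up to 29. The loss allowance is 29 - 24 = 5 subjects, or 5/29 = 17.2%. The number outside PP could be larger, because 10.3.3 does not grade deviations, although 5.5 speaks of major ones.

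**2. The adherence cut-off.** Dosing is once nightly for 14 days (6.1.3). One missed night gives 13/14 = 92.9%, which passes. Two give 12/14 = 85.7%, which fails and removes all of that subject's exploratory values.

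**3. What has been collected by then.** Under 1.3 and 7.7.2, BCVA, IOP, staining and vital signs are measured at day 7. A subject eliminated after that visit has post-baseline values that PP discards. The OCI is planned only at baseline and the final visit (1.3, 7.4.5.12, 7.7.3; Board 3 in 7.6.2 marks baseline only), so there is no day-7 OCI to lose.

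**4. What adverse event reporting recovers.** Threshold breaches are AEs, and so is a deteriorated test result "that is related to symptoms or that results in a change in study treatment or concomitant treatment or discontinuation of study medication". Examples that stay below the thresholds when asymptomatic are:
- IOP: AE from 24 mmHg (7.4.5.1). A rise from 10 to 21 mmHg stays within both the entry range (5.1.1) and the reference range (7.4.4).
- BCVA: AE from a two-line loss (7.4.5.6). A one-line loss does not reach it.
- Staining: AE from grade 3 (7.4.5.8). A change from 0 to 2 does not reach it.
- OCI: no AE threshold is given.
- Vital signs: limits are set in 7.4.5.2 and 7.4.5.3, but 8.5.2.4 narrows them: "Not all abnormal vital signs qualify as AE" unless there are symptoms or a treatment change.

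**5. Effect on the mean.** Suppose all 29 dosed subjects have a value, the 29 - k retained average m, and the k excluded average m + D. Then

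all-treated mean - PP mean = [(29 - k)m + k(m + D)]/29 - m = kD/29.

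D is an assumption throughout; the documents give no value.
- OCI, D = 10 points on the 0-100 scale: 10/29 = 0.34 (k = 1), 30/29 = 1.03 (k = 3), 50/29 = 1.72 (k = 5), and only if an OCI is obtained from these subjects.
- IOP, one excluded subject rising 21 - 10 = 11 mmHg while the others average no change: 11/29 = 0.38 mmHg.
- BCVA, one line = 0.1 logMAR (16.4): 0.1/29 = 0.003 (k = 1), 0.5/29 = 0.017 (k = 5).
- Staining, D = 2: 2/29 = 0.07 (k = 1), 10/29 = 0.34 (k = 5).

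If exclusion is unrelated to the variable, the expected D is 0 and so is the expected shift. If subjects are replaced under 5.2.2, the number dosed can exceed 29 and the divisor grows with it.

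**6. Effect on the maximum.** If the excluded subject's change is 11 mmHg and the largest retained change is M, the reported maximum change falls by 11 - M when M is below 11, and otherwise not at all. M is unknown.

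**The case against.** The strongest reply is that safety is already covered. Section 8.3 calls for every unwanted manifestation to be reported, related or not. The AE-based primary and secondary variables use everyone dosed. The five measures are exploratory and carry no decision rule. Most of this stands: the tiering is the sponsor's choice, and AE reporting is a substantial safeguard. But the AE variables are incidences, and they do not return the measured values that 10.3.1 says will be summarised.

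A second reply is that 10.3.1 may already promise descriptive tables for everyone entered, with 10.3.3 restricting only the tests. That reading is possible. It is not secure, because 10.3.1 names no set and 6.4 bars low-adherence subjects from the evaluation of exploratory variables without separating description from testing. It shows that the text needs reconciling.

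A third reply is that 5.5 may already make the withdrawal visit the final visit, at which 7.7.3 schedules the OCI. The conditional sentence there can be read as covering those who leave for reasons other than consent withdrawal or major deviation, or as covering exactly those who leave for these reasons. The point cannot be settled from the text.

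Two stronger readings of the AE gap should be resisted. A reader might infer that an asymptomatic IOP of 23 mmHg would go unrecorded. Section 8.2 also counts any unfavourable sign as an AE, and 23 lies outside the 10-21 reference range, so that is arguable; hence the example above stops at 21. A reader might also infer that eye tiredness, an OCI item missing from the event list in 7.4.5.9, would be lost. That list gives events known from the literature and does not limit recording; reported tiredness is an AE under 8.2 and 8.3.

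**Conclusion.** The point holds as a minor one. As written, the plan leaves the excluded subjects' numerical values out of the analysis of five stated safety or tolerability measures, including day-7 values for four of them. Because intolerance and certain serious adverse events lead to elimination, the omission can be informative. The loss is confined to those values, chiefly asymptomatic sub-threshold changes and the OCI score.

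Its size cannot be derived from the documents. kD/29 rests on an assumed D and on 29 dosed subjects with values, with k = 5 at the plan's own loss allowance.

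Three further inferences are not supported. First, the maximum need not fall by the excluded subject's full change, since that depends on the retained values. Second, the plan's 0.09 AE per subject (10.1.1) gives 0.09 x 29 = 2.6 as an expected count, not a ceiling on AE-driven exits. Third, nothing here touches the primary hypotheses, photophobia, pupil diameter or near acuity, all of which are analysed in everyone dosed.

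**What to change.** - In 10.3.3 and 6.4, make the safety population of 10.3.2.1 the main set for distance BCVA, IOP, staining, vital signs and the OCI, using every available post-baseline value, including day 7 and any withdrawal visit.
- Keep PP as a sensitivity analysis, and report the number excluded from it with the reason for each.
- Reconcile 6.4, 10.3.1, 10.3.2.1 and 10.3.3 so that one set is named for each output.
- Reconcile the ambiguous sentence in 5.5 with 7.4.5.12 and 7.7.3, so that it is clear whether the OCI is collected at a withdrawal visit. Changing the set alone restores the OCI only for subjects who reach a final visit.

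The cost is analysis-plan wording, a clarifying sentence in 5.5, one more table set and, if so decided, a short questionnaire at a withdrawal visit. The sample size does not change.

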6.3 Concomitant treatments and medications (permitted and prohibited)

Any medication that is used, in addition to appearing in the clinical note, must be registered in the concomitant medications section of the eCRF.

Allowed medications:

- Ophthalmic:

All permitted medications applied via ophthalmic medication during the study must wait a minimum period of 10 minutes from the last application of the treatments under study or reference. The above is to avoid the interaction of treatments in the tear film, based on the flow index and physiological tear volume. [26]

- o Tetracaine 0.5%
- o Tropicamide 0.8% /Phenylephrine 5%
- o Hypromellose 2%
- o Fluorescein
- o Lysmine Green

Prohibited Medications:

- Any ophthalmic medications that are not on the list of allowed medications
- Any systemic medication

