8.5 Responsibilities of the researcher

It is the responsibility of the Investigator to verify AEs through questioning, pertinent physical examination, assessment of evolution, as well as appropriate medical and pharmacological management; as well as to follow up until the resolution or outcome and definitive discharge of the AE, following the definitions determined in national and international regulations. [36] [47] [48]

In the event of an AE or any event that puts the health and well-being of the subjects at risk, pertinent medical care will be provided, either at the research center or will be referred to the Hospital Center with the highest resolution power with which the research center has a medical care agreement. The PI will notify the sponsor's clinical monitor, according to the times established in national and international regulations. In the case of serious adverse events, it will notify the sponsor and record the corresponding information in the eCRF and in turn, inform the IRB and IC.

The attention of the AEs will be carried out according to the event care diagram (see Figure 4. Adverse Event Care).

The sponsor's final report will include the report of adverse events in compliance with current national and international regulations. [36] [47]

If the research subject debuts during their participation in the study with any chronic adverse event, such as diabetes or systemic arterial hypertension, they will be referred to the competent health professional for chronic treatment. The follow-up and termination of your participation will be in accordance with the stipulations of the ICH.

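### IOP change is worded as a safety measure but analysed only in adherent, deviation-free subjects rather than in all dosed subjects

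*Combined protocol and SAP*

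**What the plan says.** The IOP objective in section 3.1.2.3 is worded as safety: "To evaluate the safety of PRO-201 ophthalmic solution applied to the ocular surface in healthy volunteers, by assessing intraocular pressure (IOP". Best-corrected visual acuity (BCVA), ocular surface staining and vital signs are worded the same way there. Section 7.4.3 lists the changes in all four as exploratory variables.

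For exploratory variables the analysis set is per-protocol. Section 10.3.3: "The analysis of exploratory variables will be carried out in those subjects who conclude their participation without deviations from the study protocol". Section 6.4 adds that "subjects with adherence of less than 90% will not be considered for the evaluation of exploratory variables", while keeping the same subjects for the safety and tolerability variables.

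Section 10.3.2.1 defines the safety population as "any subject who has received at least one dose of the investigational product (PRO-201) regardless of adherence to it" or to the protocol. That definition stands under the primary variables. Section 10.3.2.2 carries the primary analysis over to the secondary variables, and 10.3.3 then gives exploratory variables a different population.

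Section 5.2.1 lists among the elimination criteria "No tolerability or hypersensitivity to any of the investigational drugs", and also adherence below 90%.

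Section 10.3.1 announces "a general summary of the subjects entered the study" and includes IOP change among the variables to be described, with mean, standard deviation, maximum and minimum. It assigns no analysis set to that description.

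Section 7.4.5.1 makes an IOP peak of 24 mmHg or more a reportable adverse event (AE).

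**The concern.** A safety result is normally wanted for everyone exposed. Here one is computed in a set selected by what happened after dosing: completing the study, taking at least 90% of doses and having no deviation. A subject who stops because the drop is not tolerated is among those whose safety data matter most, and is the one most likely to be left out. The plan already applies the all-dosed principle to its primary and secondary variables, so the gap follows from the exploratory label rather than from a stated reason.

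At stake is the reported distribution of IOP change, both its mean and its maximum. Raised IOP is not on the list of anticipated events in 7.4.5.9. A moderate rise that the investigator does not record as an AE would therefore show only in the IOP-change analysis.

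**Working it through.** **1. Which subjects are in which set.**

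| Subject | Primary and secondary variables (10.3.2.1, 10.3.2.2) | IOP change (10.3.3, 6.4) |
|---|---|---|
| Completes, adherent, no deviation | in | in |
| Completes, adherence below 90% | in | out (explicit) |
| Completes with any deviation | in | out (explicit) |
| Eliminated for drug intolerance (5.2.1) | in | out (likely reading) |

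The last row is an inference. An eliminated subject would not ordinarily count as concluding without deviations, but the plan does not call intolerance a deviation.

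**2. What the adherence rule means in doses.** Section 6.1.3 gives 14 evening applications. 13/14 = 92.9% (kept) and 12/14 = 85.7% (out). Two missed evenings remove a subject from the IOP analysis, even if IOP was measured at every visit.

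**3. How many subjects might be excluded.** The plan's own sample-size step reproduces: 24 × 1.20 = 28.8, rounded up to 29 (10.1.2). This allows 29 − 24 = 5 losses. The plan gives no exclusion rate, so I take k = 0 to 5 of 29 as an assumed range.

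**4. Which rises have no other route into the results.** Entry IOP is 10 to 21 mmHg (5.1.1), and the AE rule starts at 24 mmHg (7.4.5.1). In whole mmHg, the largest rise that triggers no rule is 23 − 21 = 2 from the top of the entry range and 23 − 10 = 13 from the bottom.

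**5. Effect on the mean.** With N dosed and k excluded:

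all-dosed mean − per-protocol mean = (k/N) × (mean change in the excluded − mean change in the rest)

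For N = 29 and each 1 mmHg of difference:
- k = 0: 0
- k = 1: 1/29 = 0.03 mmHg
- k = 5: 5/29 = 0.17 mmHg

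For one excluded subject with a rise from step 4, assuming zero mean change in the other 28 and a post-baseline value for all 29:
- rise of 2 mmHg: 2/29 = 0.07 mmHg
- rise of 13 mmHg: 13/29 = 0.45 mmHg

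The per-protocol mean is 0 in both cases.

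**6. Effect on the maximum.** If exclusions were unrelated to IOP (assumption), the subject with the largest right-eye rise would be missing from the per-protocol maximum with probability k/29: 0% for none, 3% for one, 17% for five. If exclusion is related to drug effects, these figures do not apply.

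**The case against.** The strongest reply is that the important signal is already covered. Any IOP of 24 mmHg or more is a mandatory AE report. Because raised IOP is not on the anticipated list, an event judged related counts toward the primary endpoint in every dosed subject. The investigator may also record a lower value as an AE, and the reference range in 7.4.4 stops at 21 mmHg. This stands. A reader might infer that large pressure rises can vanish from the results, but the documents do not support that.

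Second, nothing is decided on IOP change. The hypotheses in 3.2 concern unexpected related AEs and photophobia only, and none of the early-termination grounds in 11.3 names IOP. This also stands and keeps the severity low.

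Third, the bias need not flatter the product. Dropping intolerant subjects may hide a rise, but dropping subjects who missed doses removes the less exposed and may make a drug effect easier to see. A reader might infer that the per-protocol result must look better than the all-dosed one. The documents give neither an exclusion rate nor any evidence that excluded subjects would have higher pressures.

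Fourth, removal of intolerant subjects is not explicit. Section 5.5 treats the withdrawal visit as the final visit for some early leavers, and its wording is unclear. Exclusion is the likely reading of 5.2.1 with 10.3.3, not a stated rule.

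A further inference is tempting: that a subject treated for raised IOP is excluded because of that treatment. Section 8.5 calls for "appropriate medical and pharmacological management" of AEs, section 6.3 prohibits "Any ophthalmic medications that are not on the list of allowed medications", and no pressure-lowering drug is listed as allowed. But the plan does not define a deviation or say that medically indicated treatment is one, and a subject treated for a pressure of 24 mmHg or more would already be a reported AE. I do not rely on this.

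The general summary in 10.3.1 does not remove the problem, because no analysis set is attached to it.

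**Conclusion.** The point holds in limited form. On the current text, IOP change is restricted to deviation-free completers with at least 90% adherence, although the plan words it as safety and defines its safety population as all dosed subjects. The exposed gap is a rise ending below 24 mmHg in an excluded subject, not recorded as an AE.

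One such subject would shift the all-dosed mean by 0.07 to 0.45 mmHg and could be missing from the maximum. The upper figure needs a rise from 10 to 23 mmHg that the investigator does not call an AE. These sizes rest on 29 dosed subjects with post-baseline values, zero mean change in the other 28, and whole-mmHg readings. The number of exclusions (0 to 5) is assumed from the loss allowance.

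The direction of bias is uncertain, and no trial conclusion or stopping rule depends on the result. This is a cheap improvement of low severity, not a flaw that undermines the study.

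**What to change.** In 10.3.3, state that IOP change, and likewise BCVA, staining and vital signs, will be described and tested in all subjects with at least one dose and at least one post-baseline value, including any value from a withdrawal visit, with the per-protocol result as supplementary. State there that this set also applies to the IOP summary in 10.3.1.

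In 6.4, say that the 90% adherence exclusion does not apply to these safety measures.

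In the report, give the number of subjects in the all-dosed set but outside the per-protocol set, with reasons.

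The cost is one or two sentences in 10.3.3, a clause in 6.4 and an extra column in the tables. No new measurement is needed: IOP is already scheduled at Days 7 and 16 (7.6.2), so a subject excluded for adherence or for a deviation after Day 7 normally has a value.

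There are two limits. Less-exposed subjects may slightly dilute a drug effect, which is why the per-protocol result stays beside the main one. A subject who leaves before Day 7 with no IOP reading still cannot be included, since unscheduled visits (7.7.5) do not specify IOP and 10.4 provides no imputation.
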